- From the initial assessment: Age, waiting time from notification to the first time offered and weight and length.
- After one month: Number of visits during the first month and weight after one month. In total, information about 60 patients was collected.

What the working group found was:

- The age is the same, 15.0 years, at start of treatment.
- How quickly you can offer time for the first visit varies between units. For three units it was around three weeks (19.6, 22.3 and 23.7 days respectively). For the other three units around two weeks (12.1, 15.1 and 15.6 days respectively). The working group has agreed that a waiting period of more than two weeks is not acceptable.
- The number of visits during the first month looks quite similar. An average of 6.2 (between 4.7 and 7.6) is just over a visit a week, which seems reasonable since it means on average more than one visit a week. Some of these visits prove to be visits within day care.

- The weight gain for the whole group was on average 0.98 kg, but some patients had lost weight. The range was -4.2 kg -6.0 kg. Of the patients that had a weight below 90%EBW at start of treatment 23.7% gained 2 kg or more during the first month of treatment.
- How much the patients have gained weight during the first month varied between the different units. The average weight gain varied between 0.1 kg and 1.5 kg between the units. It is lower than 2.0 kg, which is the lowest level of weight gain during the first month that international research has proven to be indication of a better prognosis.

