# Treatment during the first month.

The treatment focusses with high intensity on medical stabilization and weight gain from the first visit. The goal of the treatment during the first month is a weight gain of at least 2 kg (exception made for atypical anorexia nervosa with a normal or high weight - where the goal is to achieve medical stabilization).

- The treatment always begins at the first visit. Both parents receive "parental allowance for a seriously ill child".
- The patient is put on sick-leave from school. It is important to reconsider this decision at every visit to minimize the time the patient is excluded from their natural social context. As soon as possible a gradual return to school should be instigated.
- At the first visit the clinician must clarify that the patient is suffering from a serious, life threatening condition, far too severe to be managed by the young person him- or herself. Then, the clinician has to charge the parents with the full responsibility for what their child should eat and to support all the meals.
- The treatment should focus on helping the parents to support each other with the difficult task of helping their child to eat.
- Parents should, if necessary, limit excessive physical activity.
- Following the first visit, a maximum of one week should pass until the second visit.
- Physical assessments should be done at least weekly.

- If the patient has lost weight at the second visit, a family meal shall be scheduled within a few days.
- If the patient has not gained weight at the third visit, a second family meal is scheduled.
- If the patient has not reached the target weight gain during the first month, the Regional Eating Disorder Service (RSÄ) may be contacted for a case discussion.

Family meals may be arranged in day care settings, at home visits or at the outpatient clinic. The crucial element in the family meal is to help the parents to be more able support their ill child emotionally and help the child to eat food such as the parents believe their son or daughter needs. For guidelines on implementing the family meal, please see the manual.

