# Research and evaluation

#### Scientific issues

There are four central issues regarding research and evaluation.

- 1. Are the prerequisites for implementing the guidelines for RAKETSTART optimal? The investigators want to make an assessment of how the clinicians who will carry out the treatment in the project will experience opportunities and difficulties.
- 2. Are the waiting times shortened and are the recommended treatment intensity maintained? An important part of the study is to see if the healthcare system can improve its care for these life-threatening conditions.
- 3. Are the patients improved in the expected extent? The amount of patients that gained 2 kg or more before the project has been 23.7% which means that a greater proportion than that of the intervention group should gain 2 kg or more during the first month of treatment. In a study of FBT 35% of the patients gained 1.8 kg during the first 4 weeks (4), which should be the proportion that the investigators aim for.

One particular issue will be to evaluate the effect of family meals that will only be offered to those patients who do not gain weight as expected. The importance of family meals has been very sparingly evaluated in international research (15).

4. Is the financial burden for family and health care reasonable in relation to the effect? Project ROCKETLAUNCH involves an intensive treatment, which places great demands on both healthcare practitioners and the patient and family. In order to safely justify that this effort is reasonable, the investigators are making a health economic evaluation.

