#### The intervention group.

The same data as for the former patients will be collected:

- The first visit: Age, waiting time from notification to the first time offered and weight and length.
- After one month: Weight. Number of visits to reception and number of visits with family meal. Amount of in-patient care. If the family and patient have been in day care or in-patient care, days of admission will be counted.
- After one year: Weight and length and diagnostic status. Amount of in-patient care. The course of the eating disorder is primarily intended to be followed via the national quality register "RIKSÄT", and the additional modules that will be there. The supplement to RIKSÄT is called the FEDiCS (Feeding and Eating Disorder Clinical Support System). What is included is:

EDDA Standardized diagnostic interview based on DSM 5, which is making the interviewer able to make an eating disorder diagnosis. It can be used from the age of 12. (Prepared by RIKSÄT).

MINI kid (16). A diagnostic interview on other psychiatric conditions.

EDE-Q (Eating Disorder Examination - questionnaire) (17). A self-assessment form for eating disorder symptoms. For patients from the age of 12.

PSR (Psychiatric Status Rating Scale) (18). Clinical assessment of the severity of the eating disorder and if the eating disorder is in remission. Rating is made by the interviewer.

RCADS-C (Revised Children's Anxiety and Depression Scale and Subscales) (19, 20). A self-

rating questionnaire which is a screening for symptoms of anxiety, obsession, compulsion and depression. For patients from the age of 12 years.

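### The protocol promises the effect of family meals, but its own rule gives meals to patients who are losing or not gaining weight, so that effect cannot be read from a meal v no-meal or a before/after comparison

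*Protocol*

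**What the plan says.** Item 3 under Scientific issues asks whether patients improve as expected. As a particular issue within that item, the investigators want to "evaluate the effect of family meals that will only be offered to those patients who do not gain weight as expected", a topic they describe as little studied.

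The section Treatment during the first month fixes who gets a meal:
- The trigger for the first meal reads: "If the patient has lost weight at the second visit, a family meal shall be scheduled within a few days".
- A later weighing governs a further meal: "If the patient has not gained weight at the third visit, a second family meal is scheduled".
- On timing, "Following the first visit, a maximum of one week should pass until the second visit".
- On the outcome, "The goal of the treatment during the first month is a weight gain of at least 2 kg", with an exception for atypical anorexia nervosa at normal or high weight.

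Under Data Collection, the one-month items for the intervention group are weight, in-patient and day care, and "Number of visits to reception and number of visits with family meal". The same items are listed for earlier patients. The Outcome section names earlier patients as the comparator for the main outcome variables. No comparator is named for family meals.

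**The concern.** The aim is causal, but exposure is decided by the patient's own early weight change. That change falls in roughly the first week of the month over which weight gain is judged, so exposure and outcome share a component. The rule also leaves no group of triggered project patients without a meal to serve as controls.

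Two comparisons come readily to hand from the data described. One relates the meal count to one-month gain. The other looks at weight gain before and after the meal. The first sets patients selected for poor early gain against the rest. The second starts from a weight selected for being low and so picks up regression to the mean. A little-studied intervention could then be reported as harmful or helpful according to the contrast chosen, whatever the meals do.

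**Working it through.** The protocol gives no effect size, standard deviation (SD) or sample size for this question, so there is no figure to reproduce. The check asks what each comparison would show if meals had exactly no effect.

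**Inputs from the protocol (Introduction, patients before the project)**
- Mean: "The weight gain for the whole group was on average 0.98 kg, but some patients had lost weight" (60 patients).
- Spread: "The range was -4.2 kg -6.0 kg". The expected range of 60 normal values is about 4.64 SD, so SD ≈ (6.0 + 4.2)/4.64 = 2.2 kg.
- 23.7% of those below 90% of expected body weight gained 2 kg or more. If the 0.98 kg mean is applied to that subgroup (an assumption), SD ≈ (2 − 0.98)/0.716 = 1.4 kg.

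**Assumptions, varied**
- One-month SD of 1.3 to 2.2 kg.
- Weekly visits.
- Share of variance due to a stable individual slope, 0 to 100%.
- Weighing error SD of 0 to 0.7 kg.

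**One case by hand** (SD 1.8 kg, independent weekly changes, no weighing error)
- Weekly mean m = 0.98/4 = 0.245 kg. Weekly SD s = 1.8/√4 = 0.9 kg. m/s = 0.272.
- Share triggered at visit 2: Φ(−0.272) = 0.393. Density φ(0.272) = 0.384.
- Mean week-1 change if triggered: 0.245 − 0.9 × 0.384/0.393 = −0.64 kg.
- Mean week-1 change if not triggered: 0.245 + 0.9 × 0.384/0.607 = +0.81 kg.
- Later weeks are the same in both groups. Whole-month difference, meal minus no meal: −0.64 − 0.81 = **−1.45 kg**.
- Weekly gain after minus before the meal: 0.245 + 0.64 = **+0.88 kg**.
- Difference in gain counted from visit 2: **0**.

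The same patients, with no meal effect, thus give apparent harm, apparent benefit or nothing, depending on the contrast.

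**Simulation** (400,000 patients per setting, meal effect zero, trigger = loss at visit 2). The first four rows cover 30 settings: SD 1.4, 1.8 or 2.2 kg, stable share 0 to 100%, weighing error 0 or 0.3 kg.

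| Quantity | Result with no true effect |
|---|---|
| Whole-month gain, meal minus no meal | −1.1 to −3.6 kg, negative in all 30 |
| Share reaching 2 kg, meal v no meal | 0–16% v 31–50% |
| Weekly gain, after minus before the meal | +0.3 to +1.1 kg; 0 only if each patient's weekly change is constant and weighed without error |
| Gain from visit 2, meal minus no meal | −2.7 to +0.2 kg |
| Gain from visit 2, stable slopes, weighing error 0.4 or 0.7 kg | SD 2.2: −1.44, −0.34; SD 1.3: −0.25, +0.57 kg |

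Mid case (SD 1.8 kg, half of the variance stable, error 0.3 kg): one-month gain −0.10 v 1.65 kg; 2 kg reached by 9% v 41%; weekly change −0.58 kg before the meal and +0.16 kg after.

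A further zero-effect run gave about −1.0 to −3.1 kg for the whole month, 0.5 to 1.1 kg per week before/after, and −1.5 to +0.6 kg from visit 2.

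**Can the visit-2 cut-off rescue an effect estimate?** Only in part.
- Within ±0.1 kg of zero change, the no-effect difference in later gain shrank to between +0.04 and −0.30 kg. It was largest when slopes were fully stable.
- With weighing error of 0.4 to 0.7 kg, only about 7–12% of patients fall in that window. At about 150 patients a year over two years, that is 300 × 0.07 = 21 to 300 × 0.12 = 36 patients.
- Gain from visit 2 covers three of the four weeks. Scaling the SD by √(3/4) gives 1.13 to 1.91 kg. With equal halves and 80% power at two-sided 5%, the detectable difference is 2.80 × 1.13 × √(4/36) = 1.1 kg to 2.80 × 1.91 × √(4/21) = 2.3 kg. The mean gain over the whole month was 0.98 kg.
- If the visit-3 rule also applies to patients who had no first meal, 33–40% of those just above the cut-off would still get one. The protocol speaks of a second meal there, so this is a reading of the rule.

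**The case against.** The strongest reply is that the protocol commits to neither criticised comparison. It says only that the effect will be evaluated, and the analysis of a sub-question may be set out in a statistical analysis plan that is not shown. It also states the selection openly, in the same sentence as the aim. The data are probably better than the one-month list suggests: physical assessments are at least weekly, weight is regularly monitored, a standardised somatic-course form is used, and therapists complete a fidelity questionnaire for each family. Meal visits are also counted in earlier patients. The question is not among the main outcome variables.

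Most of this stands, and it limits the point. A reader might infer that the planned result will be wrong, or that it will show harm. The documents support neither inference. No contrast is planned in the text, and apparent harm is assured only for whole-month gain. With gain counted from visit 2, the bias can vanish or reverse.

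The reply does not remove the mismatch between aim and design. The aim and the trigger rule are both fixed in the protocol. An analysis plan can choose an estimator, but it cannot supply triggered project patients who were meant to go without a meal. Earlier patients who met the same trigger would differ by the whole programme as well as by the meals, and their early weights are not among the items listed.

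**Conclusion.** The concern holds as a design point. The protocol claims a causal answer that its allocation rule does not support. With no true effect, meal v no-meal on whole-month gain would show about 1 to 3.6 kg less gain with meals. Before/after would show about 0.3 to 1.1 kg per week more. Gain from visit 2 could be biased in either direction. Against a mean one-month gain of 0.98 kg, these are large.

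The direction of the whole-month bias follows from the rule and did not depend on the settings tried. The before/after bias needs only some week-to-week variation or weighing error. The sizes rest on assumed SDs, variance shares and weighing error. Only the mean, the range and the 23.7% come from the protocol, and they describe patients before the project. The point does not touch the main comparison with earlier patients.

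**What to change.** - Reword the aim under Scientific issues, item 3, as a description of who receives family meals and how they then fare. State that meal v no-meal and before/after-meal contrasts will not be read as effects.
- Add the weights at visits 1 to 3 and the dates of family meals to the intervention group's data items, taken from the records.
- If an effect is still sought, label it exploratory. Model gain from visit 2 to one month as a function of the visit-2 weight change, with a step at the trigger. Compare by whether the visit-2 trigger was met, not by meal received, since patients just above it may get a meal at visit 3.
- Present any comparison with earlier patients who met the same trigger as support only, because it also carries the rest of the programme. It would need their early weights from the case records.

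The cost is a change of wording and a few extra items from records that probably already hold them. The downside is that the comparison across the trigger is imprecise and probably cannot support a firm conclusion. The clinical trigger rule is unchanged.

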#### Methods

# **Participants**

The inclusion criteria for the patients are that they fulfill one of the three diagnoses Anorexia Nervosa, Atypical Anorexia Nervosa or ARFID and that they are in a pronounced starvation. All patients and their parents that are offered treatment within the ROCKETLAUNCH project and that fulfill the inclusion criteria will be asked to participate in the research. The treatment will take place at Child and Adolescent Psychiatry in the Southern Healthcare Region in Sweden. The Eating Disorder units in Skåne, Halland and Blekinge will participate in the project, AnorexiBulimiCenter in Kalmar and Västervik will also be involved in the project. This means that all patients with severe restrictive eating disorders in Skåne, Halland, Blekinge and Kalmar can be asked to participate in the project. In all it is 12 different out-patient clinics that will give the treatment.

At each out-patient clinic data from the 10 previous patients will be gathered in order to compare the treatment as usual with the ROCKETLAUNCH intervention.

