# Education and training

In order for the therapists to be able to work according to the guidelines developed, the investigators have to carry out training in the method. The training will be held by [name] and [name]. What is planned so far is:

- 6 training days for all those who work with these patients, who are planned to be implemented during the first year, and will be located in Lund for those who work in Skåne. In Halmstad for those who work in Halland. In Karlskrona for those who work in Blekinge. In Kalmar for those who work in Kalmar County.
- Seminars on the guidelines in smaller groups in the workplaces, which are planned on the basis of how education and competence among the staff looks at the individual workplace.
- Training around family meals with those who work in the same workplace, and co-training with other units so the investigators can know that the patients are offered the same treatment.

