#### **Data Collection**

# Patient that had been in treatment before ROCKETLAUNCH

Data from the patients who have been in treatment before the project started and meet the medical inclusion criteria will be collected. Data from ten patients at each participating unit on will be collected from the case records.

- The first visit: Age, waiting time from notification to the first time offered and weight and length.
- After one month: Weight. Number of visits to reception and number of visits with family meal. Amount of in-patient care. If the family and patient have been in day care or in-patient care, days of admission will be counted.
- After one year: Weight and length and diagnostic status. Amount of in-patient care. The information about patients before the start of the project will be collected from the same time period at all units.

The data from this early group will be compared with the collected data from the group that will participate in the project.

Weight is regularly monitored in the treatment according to the protocol. These data will include 120 patients from before the project start and approximately 150 patients annually who will enter the project.

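### The comparison window is undated, and one-year follow-up of the pre-project patients need not end before the project starts

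*Protocol*

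**What the plan says.** The number of clinics is fixed under Participants: "In all it is 12 different out-patient clinics that will give the treatment". The same section defines the treatment-as-usual group: "At each out-patient clinic data from the 10 previous patients will be gathered in order to compare the treatment as usual with the ROCKETLAUNCH intervention".

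The data-collection section on patients treated before the project sets two timing conditions. The first is being in treatment before the start: "Data from the patients who have been in treatment before the project started and meet the medical inclusion criteria will be collected". The second is a common calendar period, with no dates: "The information about patients before the start of the project will be collected from the same time period at all units". It gives the expected numbers: "These data will include 120 patients from before the project start and approximately 150 patients annually who will enter the project". The one-year variables are listed as "Weight and length and diagnostic status. Amount of in-patient care", and the section says the data of this group will be compared with those of the project group. The Outcome section names the amount of in-patient care among the main variables for that before/after comparison.

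On rollout, Education and training plans "6 training days for all those who work with these patients, who are planned to be implemented during the first year". The Supervision section has supervision running at the workplaces throughout the three years. Aim of the project notes that treatment directed at normal eating goes on beyond month one.

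**The concern.** A before/after comparison needs a before period that is free of the intervention for as long as the outcome takes to accrue. For weight after one month, that is one month. For in-patient care, weight and diagnostic status at one year, it is twelve months. The Protocol requires only that comparison patients were in treatment before the project started. A patient first seen shortly before the start meets that condition, yet spends most of the follow-up year at a clinic that is already being trained and supervised.

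The one-year outcomes bear directly on the project's stated purpose, which is better prognosis and less in-patient care. If the project works and some of its effect reaches comparison patients who are still in care, the one-year difference is likely to shrink towards zero. Analysis cannot fully recover an unexposed comparison year afterwards.

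**Working it through.** **Inputs.** 12 clinics and 10 comparison patients per clinic (Participants); 120 comparison patients and about 150 project patients a year (data collection, pre-project patients); 12 months of follow-up (same section).

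**The Protocol's own figure.** 12 × 10 = 120, which reproduces exactly.

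**Assumptions that the Protocol does not state.** The ten are counted back from project start, pre-project flow equals the expected project flow, and entry is even over time and across clinics.

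**Entry window.** Flow per clinic = 150/12 = 12.5 a year. Window W for ten patients = (10/12.5) × 12 = 9.6 months.

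**Follow-up after project start.** A patient who entered u months before the start has max(0, 12 − u) months of follow-up after it. Averaging over u from 0 to W, the share of the 12 months is
- 1 − W/24 when W ≤ 12 months;
- 6/W when W > 12 months.

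At W = 9.6 the share is 1 − 9.6/24 = 0.60, or 7.2 of 12 months. Because W is below 12, every one-year assessment falls after the start. More than half the follow-up falls after the start for those with u < 6, which is 6/9.6 = 62.5% of patients.

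**Sensitivity to flow (assumed values).**

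| Patients per clinic-year | W (months) | Share of follow-up after start | One-year assessments after start |
|---|---|---|---|
| 6 | 20 | 6/20 = 30% | 12/20 = 60% |
| 8.33 (100 in all) | 14.4 | 6/14.4 = 42% | 12/14.4 = 83% |
| 10 (120 in all) | 12 | 50% | 100% |
| 12.5 (150 in all) | 9.6 | 60% | 100% |
| 20 | 6 | 1 − 6/24 = 75% | 100% |

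The share exceeds one half only when flow is above 120 a year in all.

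**One-month outcomes.** Only patients who entered in the last month before the start overlap: 1/9.6, about 10%.

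**Effect of a gap.** At the stated flow, with the last comparison entry g months before the start (g ≤ 12), the mean follow-up after the start is (12 − g)²/(2 × 9.6) months when 12 − g ≤ 9.6. For g = 3 this is 81/19.2 = 4.2 months (35%), for g = 6 it is 36/19.2 = 1.9 months (16%), and for g = 12 it is zero. With g = 12 the entry window runs from 12 + 9.6 = 21.6 to 12 months before the start.

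**The case against.** A reader might infer that the comparison group was seen just before the project and that its one-year comparison is therefore contaminated. The Protocol does not support that, for these reasons.

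- **The window is not stated.** Participants says only that the ten are previous patients, and the data-collection section asks for one common period across units. Counting back ten patients at each clinic gives a common period only if clinic volumes are similar, so that rule fits the count-back reading poorly. An older window is also possible. The Introduction describes a mapping of ten patients per unit who entered before 20 November 2016, and Scientific issues quotes its 23.7% as the rate before the project. One-year follow-up from that window would end by November 2017. The only later date marker is a 2019 ethics number, so overlap would probably be nil.
- **Overlap in calendar time is not exposure.** The programme is defined as intensive treatment in the first month, the family therapy manual covers that month, and family meals are triggered at the second and third visits. About 90% of comparison patients would be past that month at the start. Training is spread over year one, so teams may not be fully trained while the overlap runs.
- **The only quantified target is a one-month one.** One-month weight, waiting time and visit frequency are nearly untouched, and in-patient care is also recorded at one month.

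All of this stands as a limit on the point. It does not remove it. The 2016 mapping covered 60 patients at six units and recorded only first-visit and one-month data. The Protocol describes collection still to come, from 12 clinics, under the medical inclusion criteria and with one-year data. The plain reading of the Participants sentence remains the most recent ten, which is also how the earlier mapping was done. Nothing in the text rules it out.

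**Conclusion.** The point holds conditionally. The Protocol leaves the comparison window undated and does not require the comparison year to close before the project opens. If the ten are the immediately preceding patients and flow before the project was like the stated flow, about 60% of their follow-up (30% to 75% over 6 to 20 patients per clinic-year) falls after the start. At the stated flow, so do all 120 one-year assessments. Any bias would probably run towards no difference in one-year in-patient care, weight and diagnostic status. Its size cannot be derived, because the Protocol gives no measure of how far later care at a clinic in training departs from earlier care. The one-month comparison is essentially sound on this point.

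**What to change.** In Participants and in the data-collection section on pre-project patients:

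1. State the calendar window, with the project and training start for each clinic. Say how ten patients are chosen within the common period where clinic volumes differ.
2. For the one-year outcomes, use the last ten eligible patients per clinic whose first visit was at least 12 months before project and training start. This brings the overlap to zero.
3. The most recent ten may be kept for the one-month outcomes, where closeness in time is an advantage and overlap is small.

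The data come from case records, so the cost is modest: no extra records if one set serves both purposes, and up to 12 × 10 = 120 more if two sets are used. The real price is a one-year comparison group from about a year earlier, with somewhat more room for calendar-time differences. That should be acknowledged in the text.
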